with medication compliance procedures; and pregnancy tests for female subjects as it may not be advisable for pregnant women to lose weight. 3) Weight (**Wt**) measurement to the nearest 0.5kg and height (**ht**) will be measured to calculate **BMI**. Waist circumference (**WC**) will be measured with a tape measure placed on the midpoint between iliac crest and lowest rib rounded to the nearest 5 mm. Resting blood pressure (**bp**) and pulse will be measured. Our lab has established procedures for calibrating scales (National Institutes of Standards and Technology Certified weights) and waist measurement. The lab conducts reliability exercises for waist measurements for study stuff (ICC= 0.97, TEM=2.4%) 4) Standard Laboratory Testing (**Lab**) 5) Brief Psychiatric Rating Scale (**BPRS**) is the gold-standard overall measure of schizophrenia symptoms which will be utilized to demonstrate that the Naltrexone and/or SIMPLE intervention does not cause worsening of the illness symptoms apart from the usual fluctuations of the natural course. 6) Beck Depression Inventory (**BDI**) 21-item version is a psychometrically sound, widely used measure of the features and symptoms of depression. The BDI taps a broad range of negative affect – not just depression – and is a highly efficient measure for detecting fluctuations in broad psychopathology and distress. 7) Three Factor Eating Questionnaire (**TFEQ**) also known as the Eating Inventory is a measure of eating behaviors with three factors: dietary (cognitive) restraint, disinhibition, and hunger. The TFEQ has received psychometric support and is a frequently used measure in obesity trials. 8) The Questionnaire on Craving for Sweet or Rich Foods (**QCSR**) The QCSR is a two factor, nine item scale assessing the presence of cravings for rich and sweet foods and has been found to have good psychometric properties. 10) The Yale Physical Activity Survey (**YPAS**) is an interview-administered questionnaire that assesses activity participation in number of hours/week in different categories (i.e. work, recreation, exercise) and takes about 20 minutes to complete. 11) Resting Metabolic Rate (**RMR**) is calculated through a mathematical formula not indirect calorimetry. No special procedure is utilized that would be bothersome to subjects. 12) Quality of Life Enjoyment and Satisfaction Questionnaire (**Q-LES-Q**) is specifically designed to use with schizophrenia patients and focuses on patient's subjective perception of various aspects of their life. 13) SF-36 Health related Quality of Life Questionnaire; a 36-item short-form (**SF-36**) was constructed to survey health status in the Medical Outcomes Study. The SF-36 was designed for use in clinical practice and research, health policy evaluations, and general population surveys. The SF-36 includes one multi-item scale that assesses eight health concepts: 1. limitations in physical activities because of health problems; 2. limitations in social activities because of physical or emotional problems; 3. limitations in usual role activities because of physical health problems; 4. bodily pain; 5. general mental health (psychological distress and wellbeing); 6. limitations in usual role activities because of emotional problems; 7. vitality (energy and fatigue); and 8. general health perceptions. SF-36 can be administered as a self-rating scale or by interviewer. In this study, trained rates will administer the SF-36. 14) UKU Side Effect Checklist (**UKU**) This is a comprehensive rating scale developed for psychotropic drugs and a cross-sectional study of side effects in neuroleptic-treated patients. Common adverse events related to naltrexone will be added to this scale, as needed. 15) Columbia-Suicide Severity Rating Scale (**C-SSRS126**) is a scale developed for use in clinical trials of psychoactive agents and recommended by the FDA to be used for safety tracking of medications for suicidality. 16) Cognitive Battery. Tests from the Measurement and Treatment Research to Improve Cognition in Schizophrenia (**MATRICS**) Consensus Cognitive Battery (**MCCB**): Given the cognitive impairment of schizophrenia, careful assessment of cognition is necessary for feasibility of any medication use in schizophrenia. This is a cognitive battery developed on NIMH initiative by experts from academia, pharmaceutical industry, and US government for the specific purpose of use in clinical trials in schizophrenia. Validity, reliability, sensitivity to change, and normative data is established.

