
4. Genetic Testing N/A

A. Describe

- i. the types of future research to be conducted using the materials, specifying if immortalization of cell lines, whole exome or genome sequencing, genome wide association studies, or animal studies are planned
- ii. the plan for the collection of material or the conditions under which material will be received

Assessment Schedule

SCID, Demographics, Physical exam	Week 0
Urine toxicology, pregnancy test for female subjects	Week 0 and every 4 weeks subsequently + as needed
Fluorescence check in urine for compliance	determined by study physician
Fasting Glucose, Insulin, HbA1c, Lipid Profile, Liver function tests	Week 0, 16, 32, 52
Serum leptin, ghrelin, peptide YY, adiponectin, high sensitivity	Week 0, 16, 52
CRP, interleukin 6	
Framingham Score	Calculated same time with blood draws.
Vitals (Blood Pressure, pulse)	Weekly for first 4 weeks, then every two weeks
Weight, BMI	Weekly for first 4 weeks, then every two weeks
RMR, Waist Circumference (WC), 24hr Food Recall, TFEQ, YPAS, BPRS, BDI, QCSRF, QLS, SF-36, C-SSRS.	Week 0 and every 4 weeks
UKU side effects	Weekly for first 4 weeks, then every two weeks
Cognitive Battery	Week 0, Week 16, Week 52

- iii. the types of information about the donor/individual contributors that will be entered into a database
- iv. the methods to uphold confidentiality

- B. What are the conditions or procedures for sharing of materials and/or distributing for future research projects?
- C. Is widespread sharing of materials planned?
- D. When and under what conditions will materials be stripped of all identifiers?
- E. Can donor-subjects withdraw their materials at any time, and/or withdraw the identifiers that connect them to their materials?
 - i. How will requests to withdraw materials be handled (e.g., material no longer identified: that is, anonymized) or material destroyed)?
- F. Describe the provisions for protection of participant privacy
- G. Describe the methods for the security of storage and sharing of materials

5. Subject Population: Provide a detailed description of the types of human subjects who will be recruited into this study.

200 patients with severe mental illness

6. Subject classification: Check off all classifications of subjects that will be specifically recruited for enrollment in the research project. Will subjects who may require additional

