safeguards or other considerations be enrolled in the study? If so, identify the population of subjects requiring special safeguards and provide a justification for their involvement.

 Children	 Healthy	 Fetal material, placenta, or dead fetus
 Non-English Speaking	 Prisoners	 Economically disadvantaged persons
 Decisionally Impaired	 Employees	 Pregnant women and/or fetuses
 Yale Students	 Females of childbearing potential	

NOTE: Is this research proposal designed to enroll children who are wards of the state as potential subjects? Yes No (If yes, see Instructions section VII #4 for further requirements)

Subjects must pass the following quiz (80% correct) in order to be eligible to consent for the study.

1. I will take study medication for 52 weeks/1 year in this study.	T_X_	F ____
2. This study aims to help me lose weight.	T_X_	F ____
3. I have to be in the study, even if I don't want to.	T ____	F_X_
4. I will have blood drawn in this study.	T_X_	F ____
5. I should report to the study doctor if I have any side effects	T_X_	F ____
6. I will be paid for study assessments.	T_X_	F ____
7. The study doctor and research team will know which medication I'm taking during the study.	T ____	F_X_
8. Please circle the names of the study medication that you may receive in this study.		

Haldol

Prolixin

Mellaril

Naltrexone

Paxil

Placebo

9. I can stop being in the study any time that I want.	T_X_	F ____
10. One of the possible side effects of the study medication is nausea.	T_X_	F ____
11. If I take the study medication while taking an opiate (see list on last page) I may experience withdrawal symptoms, such as nausea, vomiting, diarrhea, muscle aches, abdominal cramping, anxiety, and sweating.	T_X_	F ____

7. Inclusion/Exclusion Criteria: What are the criteria used to determine subject inclusion or exclusion?

Inclusion Criteria

- 1) Age 18 to 75
- 2) Meet DSM-IV criteria for schizophrenia, schizoaffective disorder, bipolar disorder, major depression, or another psychotic disorder based on SCID interview
- 3) Body Mass Index (BMI) of 28 and over

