Reduced efficacy of opioid medications with naltrexone: Patients taking naltrexone may not benefit from opioid containing medicines, such as cough and cold preparations, antidiarrheal preparations, and opioid analgesics. In an emergency situation when opioid analgesia must be administered to a patient taking naltrexone, the amount of opioid required may be greater than usual, and the resulting respiratory depression may be deeper and more prolonged. Study participants will carry an information card to be used in case of an emergency.

Small increased risk of depression, suicidal ideation, and suicide: Based on data from placebo controlled trials in patients with alcohol and/or opiate dependence there was observed an infrequent however small increased incidence of depression, suicidal ideation, attempts, and completed suicides in the naltrexone treated group compared to the placebo group.

Other Side Effects: In an open label safety study with approximately 570 individuals with alcoholism receiving naltrexone, the following new-onset adverse reactions occurred in 2% or more of the patients: nausea (10%), headache (7%), dizziness (4%), nervousness (4%), fatigue (4%), insomnia (3%), vomiting (3%), anxiety (2%) and somnolence (2%).

Exposure to Naltrexone during Pregnancy: Naltrexone is a pregnancy Category C medication meaning the drug should be given to patients only if the potential benefit justifies the potential risk to the fetus. There is no data on the use of naltrexone or other opioid antagonists in pregnant women. The effects, if any, on the developing fetus are unknown. We will require that female patients of child bearing age use contraception to prevent pregnancy during participation in the study and will not enroll participants who are pregnant or who are trying to get pregnant.

Urine collection

Urine specimens are collected for research assessments and should pose no appreciable risks, and will be done using established procedures already in place at CMHC.

Blood collection

Subjects participating in these studies will have multiple blood draws using established procedures in the CMHC. The blood draw has the risk of producing a bruise at the venipuncture site, and rarely development of a small infection.

Cognitive Assessments, Rating Scales and Questionnaires

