Other Outcomes: Schizophrenia symptoms (BPRS), depression (BDI), dietary consumption (TFEQ), exercise (YPAS), quality of life (Q-LES-Q and SF-36), cognition (MATRICS) and metabolism/inflammation markers will be obtained as presented in table 3. Summary statistics (frequencies, percents, means and standard deviations, and medians and interquartile ranges) will be calculated for naltrexone vs. placebo at each time point. Appropriate parametric (for normally distributed data) and non-parametric (deviation from normality in data distribution) approaches will be used to ascertain clinically meaningful group differences at each time point. Depending upon the distribution of these outcomes, the effect of naltrexone vs. placebo on change over time in each outcome will also be examined with GLMM, making appropriate model selections for either binary or continuous outcomes.

Using UKU Side Effect Checklist and C-SSRS we will list and summarize side effects and suicidal tendencies reported in each treatment group. Medication changes that could not be avoided during the study will be examined in three groups: no change, change from a higher weight liability to a lower weight liability medication, and vice versa. Weight liability rankings of antipsychotics will be based on Allison and Newcomer. Distributions of all variables will be evaluated for normality. Alternative statistical approaches such as transformations or non-parametric tests will be used, as required.

SECTION VI: RESEARCH INVOLVING DRUGS, BIOLOGICS, RADIOTRACERS, PLACEBOS AND DEVICES

A. DRUGS, BIOLOGICS and RADIOTRACERS

- 1. Identification of Drug, Biologic or Radiotracer:** What is (are) the name(s) of the drug(s) biologic(s) or radiotracer(s) being used? Identify whether FDA approval has been granted and for what indication(s).

Naltrexone is an FDA approved medication with the indication of alcohol dependence.

All protocols which utilize a drug, biologic or radiotracer **not** approved by, but regulated by, the FDA, or a radiotracer regulated by the RDRC, must provide the following information:

- a. What is the Investigational New Drug (IND) **number** assigned by the FDA? N/A
- b. Who holds the IND?
- c. All protocols which utilize a radiotracer not approved by, but regulated by the FDA must provide the IND number: _____
Alternatively, use of the investigational radiotracer may be under RDRC/RSC oversight: (check if appropriate) _____

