Subjects will be paid in cash at each in person appointment. The baseline procedures will span 3 appointments, for which they will receive \$15 each time (\$45 total). Following enrollment, subjects will be seen weekly for the first 4 weeks. They will be paid \$5 each for weeks 1-3. After the first 4 weeks, subjects will attend appointments every other week. They will be paid \$10 for these appointments and

on an escalating payment for each monthly milestone (\$15, \$20, \$25, \$30, \$35...\$70). The total amount a subject can earn for completing the entire study is \$700.

3. **Costs for Participation (Economic Considerations):** Clearly describe the subject's costs associated with participation in the research, and the interventions or procedures of the study that will be provided at no cost to subjects.

There is no cost to the subject.

4. **In Case of Injury:** This section is required for any research involving more than minimal risk.

- a. Will medical treatment be available if research-related injury occurs?
Yes, medical care will be provided for physical injury or illness that occurs as a direct result of subject participation in this study.
- b. Where and from whom may treatment be obtained?
The PI is responsible to make the necessary referrals to Yale University/YNHH clinics or patient's own primary care physician.
- c. Are there any limits to the treatment being provided?
No
- d. Who will pay for this treatment?
There are no funds available for compensation of care. The patient and/or their insurance will be responsible for treatment for any study related injury.
- e. How will the medical treatment be accessed by subjects?
Referral by the PI.

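### The schedule states no pre-dose UKU rating and the analysis has no new-or-worse rule, so the listed side-effect rates would mix existing antipsychotic effects with naltrexone effects and dilute the arm difference

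*Combined protocol and SAP*

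**What the plan says.** **Schedule.** In the Assessment Schedule (Section V), the row "UKU side effects" carries the timing "Weekly for first 4 weeks, then every two weeks". The vitals row and the weight/BMI row carry the same timing. The row for questionnaires, waist circumference, BPRS, BDI and C-SSRS reads "Week 0 and every 4 weeks". The diagnostic, toxicology, laboratory and cognitive rows also print week 0.

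**Visits.** The Research Plan (Section V, item 3) names the side-effect check among the things done at the weekly and then two-weekly visits during treatment. Section X, item 2 (Payments) places the weekly visits after enrollment. Of the earlier visits it says "The baseline procedures will span 3 appointments", without listing what is done at them.

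**Instrument and population.** The Research Plan says of the UKU: "This is a comprehensive rating scale developed for psychotropic drugs and a cross-sectional study of side effects in neuroleptic-treated patients". The inclusion criteria require every subject to be on a stable antipsychotic dose.

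**Analysis.** Under Other Outcomes (Section V, item 12): "Using UKU Side Effect Checklist and C-SSRS we will list and summarize side effects and suicidal tendencies reported in each treatment group". The UKU is not among the outcomes named for analysis of change over time.

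**Expected rates.** The Risks section (Section V, item 9) introduces the naltrexone rates with "the following new-onset adverse reactions occurred in 2% or more of the patients".

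**The concern.** The UKU was built for patients on drugs of the kind every subject here already takes, so some items are likely to be positive before the first capsule. Unless the pre-dose state is recorded, and a rule says how to use it, a report of fatigue or insomnia at week 2 cannot be separated from fatigue or insomnia that was there at week 0.

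Two things suffer. First, the listed rates are too high in every arm, and the difference between each naltrexone dose and placebo is too small. Second, the rates no longer match the yardstick. The Risks section gives new-onset percentages, and the Data and Safety Monitoring Plan (Section V, item 11) calls for reporting of anticipated events that occur more often than expected. A count that includes pre-existing symptoms cannot be set against a new-onset expectation.

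The analysis gap stands apart from the schedule gap. Even if a week-0 UKU is taken in practice, nothing in the plan says it will be used. And if none is taken, it cannot be recovered after the first dose.

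**Working it through.** The documents give no side-effect rate assumption or power figure for the UKU, so there is nothing to reproduce. The check has two parts.

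**1. Is a pre-dose UKU provided anywhere?**

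- The UKU timing prints no week 0; the row that holds C-SSRS, which is summarized in the same sentence as the UKU, does.
- Weight has the same timing as the UKU, yet must be measured before entry because of the criterion "Body Mass Index (BMI) of 28 and over". So the shared wording does not rule out a baseline.
- For the UKU no entry criterion or other section plays that part. The intake clinical history and physical examination are not item-level UKU ratings.

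Result: a pre-dose UKU is unspecified.

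**2. What follows if raw on-treatment reports are summarized?**

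Inputs from the documents: 200 subjects randomized 1:1:1, so 200/3 = 66.7 per arm; two-sided 5%; new-onset nausea on naltrexone 10% (Risks). Assumed: new-onset rate on placebo 2%; share b with the symptom at entry, 0 to 40%, equal in all arms; everyone with the symptom at entry reports it again on study.

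- Reported rate = b + (1 - b) × new-onset rate.
- Arm difference = (1 - b) × (difference in new-onset rates).

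For b = 30%: placebo 0.30 + 0.70 × 0.02 = 0.314; naltrexone 0.30 + 0.70 × 0.10 = 0.370; difference 0.056 = 0.70 × 0.08; ratio 0.370/0.314 = 1.18. In subjects, the raw listing shows about 21 on placebo (0.314 × 66.7) and 25 on naltrexone (0.370 × 66.7). About 20 in each arm (0.30 × 66.7) had the symptom at entry, which leaves about 1 and 5 new cases.

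The last two columns give the chance of a nominally significant difference for one dose against placebo. They use the usual normal approximation for two proportions, Φ[(|p1 - p2| - 1.96 × SE0)/SE1], where SE0 is the pooled and SE1 the unpooled standard error. There are 66.7 per arm for raw reports and 66.7 × (1 - b) for new-onset cases among those free of the symptom at entry.

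| b | Raw, placebo | Raw, naltrexone | Difference (points) | Ratio | Raw | New-onset |
|---|---|---|---|---|---|---|
| 0% | 2.0% | 10.0% | 8.0 | 5.00 | 49% | 49% |
| 10% | 11.8% | 19.0% | 7.2 | 1.61 | 21% | 45% |
| 20% | 21.6% | 28.0% | 6.4 | 1.30 | 13% | 41% |
| 30% | 31.4% | 37.0% | 5.6 | 1.18 | 10% | 37% |
| 40% | 41.2% | 46.0% | 4.8 | 1.12 | 8% | 32% |

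With a week-0 rating the new-onset difference stays at 8.0 points and the ratio at 5.0 for every b.

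Other assumed rates:

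- 10% against 5%, b = 30%: the difference falls from 5.0 to 3.5 points; chance 6% raw, 15% new-onset.
- 4% against 2%, b = 30%: the difference falls from 2.0 to 1.4 points; chance below 10% either way.
- 25% against 5%, b = 20%: the difference falls from 20 to 16 points; chance 51% raw, 83% new-onset. The 25% is above every rate in the Risks section.

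**The case against.** The strongest reply is that the schedule's wording gives visit frequency and says nothing about baseline. Weight proves it: same wording, yet measured before entry. This stands. A reader might infer from the table that no baseline UKU is taken; the documents do not support that. They support only that none is stated.

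A reader might also infer that a naltrexone effect would be hidden. That too goes further than the documents allow. The trial is randomized, with separate schedules by antipsychotic agent, so existing symptoms should be similar across arms. No false difference is created, and a large effect could still show, as the 25% against 5% case illustrates.

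Further points carry weight:

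- Tolerability is not among the stated hypotheses, and the UKU is a descriptive outcome with no test planned. The chances in the table therefore describe a comparison the plan does not make, and they depend heavily on the assumed rates.
- Other week-0 measures exist. The SF-36 covers fatigue and bodily pain, and the BDI covers negative affect. No week-0 measure is stated for insomnia or somnolence, and none of these scales is a UKU item rating.
- Adverse events have their own route: grading and attribution by the principal investigator, review by the safety officer, and twice-yearly tables to the monitoring board. That route would catch some effects, but attribution is a judgement, and it is weaker without a record of what the subject had beforehand.

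None of this supplies a pre-dose UKU or a rule for using one.

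**Conclusion.** The point holds as a gap in specification. The plan does not say whether the UKU is rated before the first dose, and its analysis does not separate new or worse symptoms from those present at entry. Followed as written, it yields raw on-treatment counts that are inflated in every arm, with an arm difference reduced by the factor (1 - b): a loss of 10% to 40% for b between 10% and 40%. In the illustration the risk ratio falls from 5.0 to between 1.61 and 1.12.

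The factor (1 - b) follows from the arithmetic, given equal prevalence across arms and persistence of the symptom on study. The values of b and the placebo rates are assumptions; only the 10% nausea rate comes from the protocol. The harm is dilution in a descriptive safety summary and loss of comparability with the Risks section. The primary weight analysis is not touched. The change is still worth making, because it is cheap and the pre-dose rating cannot be obtained later.

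**What to change.** 1. In the Assessment Schedule, change the UKU timing to: *Week 0 (before first dose), weekly for first 4 weeks, then every two weeks*.
2. In Section V, item 12, Other Outcomes, add a sentence: *UKU items will be summarized by arm (25 mg, 50 mg, placebo) as new or worse than the week-0 rating, alongside the listing of all reported items.*

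If a pre-dose UKU is already intended, the first change only records it; the second is needed either way.

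The cost is a few minutes of rater time per subject at one of the three baseline appointments already planned and paid for, plus one sentence of text. No visit, treatment or primary analysis changes.
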